12.0 Descriptive Factors

- 12.1 Transfusion Dependent: Yes vs No
- 12.2 MDS subcategory: MDS vs MDS/MPN overlap vs CMML
- 12.3 Previous cytotoxic chemotherapy: yes vs no
- 12.4 AML subcategory: without prior HMA vs prior HMA
- 12.5 HMA failure: refractory vs relapsed vs progressed on HMA
- 12.6 AML: De novo vs secondary AML
- 12.7 AML: newly diagnosed vs relapsed/refractory
- 12.8 MF: with or without HU

13.0 Treatment/Follow-up Decision at Evaluation of Patient

- 13.1 Patients who have not developed PD will continue treatment per protocol.
- 13.2 Patients who develop PD while receiving therapy will go to the event monitoring phase. This phase consist of obtaining follow up/survival data for up to 5 years by phone and medical record review of subjects.
- 13.3 Patients who go off protocol treatment for reasons other than PD will go to the event monitoring phase per Section 18.0.
- 13.4 If a patient in the initial safety portion fails to complete 28 days of treatment for reasons other than dose-limiting toxicity defined adverse events, the patient will be regarded as uninformative in regard and an additional patient will be treated; however, all toxicity information will be utilized in the analysis.
- 13.5 A patient is deemed *ineligible* if after registration, it is determined that at the time of registration, the patient did not satisfy each and every eligibility criteria for study entry. The patient will go directly to the event monitoring phase of the study (or off study, if applicable).
 - If the patient received treatment, all data up until the point of confirmation of ineligibility must be submitted. Event monitoring will be required per Section 18.0 of the protocol.
 - If the patient never received treatment, on-study material and the End of Active Treatment/Cancel Notification Form must be submitted. No further data submission is necessary.
- 13.6 A patient is deemed a *major violation*, if protocol requirements regarding treatment in cycle 1 of the initial therapy are severely violated that evaluability for primary endpoint is questionable. All data up until the point of confirmation of a major violation must be submitted. The patient will go directly to the event monitoring phase of the study. Event monitoring will be required per Section 18.0 of the protocol.

- 13.7 A patient is deemed ascreen failure if he/she is removed from the study for any reason before any study treatment is given. On-study material and the End of Active Treatment/Cancel Notification Form must be submitted. No further data submission is necessary.

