6.3 Safety & Expansion Portions

6.31 Correlative Research

6.311 A mandatory correlative research component is part of this study, the subject will be automatically registered onto this component (see Section 3.17 and 14.0).

6.32 At the time of registration, the following will be recorded:

- Subject has/has not given permission to store and use his/her sample(s) for future research of Acute Myeloid Leukemia or Myelodysplastic Syndrome at NYU Langone Health.
- Subject has/has not given permission to store and use his/her sample(s) for future research to learn, prevent, or treat other health problems.
- Subject has/has not given permission to give his/her sample(s) to researchers at other institutions.

6.33 Treatment on this protocol must commence at a participating institution, NYU Langone Health, under the supervision of a hematologist.

6.34 Treatment cannot begin prior to registration and must begin \leq 14 days after registration.

- 6.35 Pretreatment tests/procedures (see Section 4.0) must be completed within the guidelines specified on the test schedule.
- 6.36 All required baseline symptoms (see Section 10.3) must be documented and graded.
- 6.37a Study drug is available on site.
- 6.37b Blood draw kit is available on site.
- 6.37c Subject questionnaire booklet is available on site; copies are not acceptable for this submission.
- 6.37d Randomization Procedures
- 6.37d1 After the subject has been registered into the study, the values of the grouping factors will be recorded. An elderly newly diagnosed AML subject will be allocated to arm A. A relapsed/refractory AML or HMA failure MDS/ AML subject will be randomized to treatment group arm B or arm C. MF patients will be allocated to Arm C but not included in the statistical analysis for Arm C, rather descriptive response rates will be summarized separately.
- Elderly (age 60+) newly diagnosed AML subjects assigned to Arm A: AZD1775 days 1-5, 8-12 and AraC days 1-5, 8-12
 - Relapsed/Refractory AML and HMA failure MDS/ AML subjects randomized to Arm B: AZD1775 days 1-5, 8-12 and AraC days 1-5, 8-12 or Arm C: AZD1775 days 1-5, 8-12.
 - MF patients allocated to Arm C

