16.4 Secondary Endpoints

- 16.41 Safety and tolerability data will be compiled. The maximum grade for each type of adverse event will be recorded for each patient, and frequency tables will be reviewed to determine patterns (by arm, disease and overall). Additionally, the relationship of the adverse event(s) to the study treatment will be taken into consideration. The rate of grade 3 or higher non-hematologic adverse events, and the rate of grade 4 or higher adverse event (hematologic and non-hematologic) will be computed each with a 95% exact binomial confidence interval.
- 16.42 Summary statistics for clinical benefit (mean and standard deviations for continuous variables and frequencies and percentages for discrete variables) will be compiled for hematologic improvements and transfusion requirements.
- 16.43 Duration of response is defined for all evaluable patients who have achieved a response as the date at which the patient's earliest best objective status is first noted to be a CR/CRi response to the earliest date progression is documented. If a patient dies subsequent to the response without a documentation of disease progression, the patient will be censored at the last date disease was assessed. In the case of a patient failing to return for evaluations before a documentation of disease progression, the patient will be censored for progression on the date of last evaluation. The distribution of duration of response will be estimated using the method of Kaplan-Meier (1958).
- 16.44 Time to response/progression is defined as the time from registration to the earliest date of documentation of response/disease progression. If a patient dies without a documentation of disease progression the patient will be censored at the last date disease was assessed. In the case of a patient starting treatment and then never returning for any evaluations, the patient will be censored for progression 1 day post-registration. The distribution of time to progression will be estimated using the method of Kaplan-Meier (1958).
- 16.45 Survival time is defined as the time from registration to death due to any cause. The distribution of survival time will be estimated using the method of Kaplan-Meier (1958).
- 16.46 Time to AML or death is defined for all evaluable patients with MDS and MF as the time from registration to leukemic transformation or death due to any cause. The distribution of time to AML or death will be estimated using the method of Kaplan-Meier (1958).

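### Registered and randomised patients who never start treatment get no survival follow-up although survival and progression are timed from registration, so these estimates may be slightly overstated

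*Combined protocol and SAP*

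**What the plan says.** - **Order of events.** A patient counts as accrued at registration (6.21, 6.23). Arm assignment comes next: "After the subject has been registered into the study, the values of the grouping factors will be recorded" (6.37d1), and relapsed/refractory AML and HMA-failure patients are then randomised 1:1 to Arm B or C (6.37d1, 16.23). On timing, 6.34 says "Treatment cannot begin prior to registration and must begin" no later than "14 days after registration".
- **Patients who never start.** Under 13.7, anyone "removed from the study for any reason before any study treatment is given" is a screen failure. On-study material and a cancel form are due, after which "No further data submission is necessary". Section 13.5 treats a never-treated patient later found ineligible the same way: "on-study material and the End of Active Treatment/Cancel Notification Form must be submitted. No further data submission is necessary". The Schema note sends non-starters to Section 13.0.
- **Patients who do start.** After progression they enter event monitoring, described as "obtaining follow up/survival data for up to 5 years by phone and medical record review of subjects" (13.2). Those who stop for other reasons also enter it (13.3).
- **Endpoints.** Section 16.45 reads "Survival time is defined as the time from registration to death due to any cause". Sections 16.44 and 16.46 use the same origin. Section 16.46 is limited to evaluable patients, and 16.22 and 16.23 make starting treatment a condition of being evaluable. Sections 16.44 and 16.45 name no analysis set. The rule in 16.44 for patients with no evaluations covers only those who started treatment.

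**The concern.** The clock and the population do not match. A patient who dies, deteriorates or declines between registration and first dose contributes no survival outcome. Every patient who does contribute was alive at first dose and is credited with the waiting time. Pre-dose deaths are thus removed from curves that claim to run from registration.

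For Arms B and C there is a second consequence. The arms differ visibly (oral drug alone, or oral drug plus twice-daily injections) and no blinding is described, so willingness to start can depend on the arm drawn. The analysis is confined to starters, and the two spare patients per arm in 16.23 cover cancellations. A difference in refusal between arms would therefore not be reflected in the selection.

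**Working it through.** **The plan's own figures.** For Arms B and C, P(at least 3 responses in 20) is 0.0755 at a true rate of 5% and 0.9087 at 25%. These round to the stated 0.08 and 0.91. Maximum accrual is 20 + 2 = 22 per arm, as stated. The plan gives no design figure for survival or progression, so there is none to reproduce.

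**Inputs for the size of the effect.**
- Median survival in HMA-failure MDS: 4.3–5.8 months (Section 1.1).
- Longest gap from registration to first dose: 14 days (6.34). The typical gap is not given, so I assume 3, 7 and 14 days.
- Assumptions: exponential survival, and the same gap d for every patient. One month is 30.44 days.

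**Formulas.**
- Share dying before first dose = 1 − exp(−ln 2 × d / median), with d in months.
- Expected pre-dose deaths per arm = 22 × that share.
- Apparent median = true median + d. Under an exponential, a patient alive at d has the same remaining median, and the wait is added on top.

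| Median (months) | Gap (days) | Die before first dose | Per 22 patients | Apparent median (months) | Overstatement |
|---|---|---|---|---|---|
| 4.3 | 3 | 1.6% | 0.35 | 4.40 | 2.3% |
| 4.3 | 7 | 3.6% | 0.80 | 4.53 | 5.3% |
| 4.3 | 14 | 7.1% | 1.57 | 4.76 | 10.7% |
| 5.8 | 3 | 1.2% | 0.26 | 5.90 | 1.7% |
| 5.8 | 7 | 2.7% | 0.60 | 6.03 | 4.0% |
| 5.8 | 14 | 5.3% | 1.18 | 6.26 | 7.9% |

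At the 14-day ceiling, six-month survival would read 0.409 instead of 0.380 (median 4.3 months) or 0.516 instead of 0.488 (median 5.8 months).

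**Does an unnamed analysis set rescue 16.44 and 16.45?** No. Without data after the cancel form, a non-starter could at best be censored near day 0, which has the same effect as exclusion.

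**Response rate, Arms B and C.** If two randomised patients do not start and count as non-responders, 3/20 = 15.0% becomes 3/22 = 13.6%. The margin in 16.23 for preferring the combination is 10 percentage points. As an illustration, 5/20 against 3/20 is a difference of 10.0 points. If two patients allocated to the combination and none allocated to the single agent had failed to start, the all-randomised difference would be 5/22 − 3/20 = 22.7% − 15.0% = 7.7 points.

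**The case against.** - **A record does remain.** A reader might infer that pre-dose deaths and refusals disappear without trace. The documents do not support that. Section 13.7 requires on-study material and a cancel form, and 6.23 requires additional sites to submit screen failures and pre-treatment withdrawals with source documentation. Non-starters can be counted. What is lost is their outcome. This objection stands against the stronger reading only.
- **Waiting time is not itself a bias.** If nobody dies before first dose, survival from registration is correct. A reader might also add the 8–11% overstatement to the 5–7% of pre-dose deaths, but these are one 14-day scenario in two units. If one of 44 randomised patients died before first dose, the shift would be −ln(1 − 1/44)/ln 2, or about 3% of the median. This stands.
- **The mortality assumption is probably high.** Entry requires ECOG 0–1 (3.14), organ-function limits (3.13) and no uncontrolled infection (3.21). Day 1 tests need not be repeated if pre-registration tests fall within 72 hours (footnotes to Tables 4.1–4.3), so short gaps are foreseen. The medians describe HMA-failure MDS, not relapsed/refractory AML. This stands, and it is why the 3 to 7 day range is the better guide.
- **No decision rule uses these endpoints.** They are secondary Kaplan-Meier estimates without a test. With 20 deaths in an arm, a rough 95% interval for an exponential median is the estimate times exp(±1.96/√20), or 0.65 to 1.55. A 2–5% shift is small beside that. This limits the importance. It does not remove a directional bias that is easy to avoid.
- **A treated-patient set is a legitimate choice in a screening study.** True, but it then calls for a clock that starts at treatment, or for follow-up of everyone from registration. The plan has neither.

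**Conclusion.** The point holds in a limited form. Followed as written, the plan drops outcomes between registration and first dose and still counts the waiting time, and no other section corrects this. Survival, time to progression and time to AML may be slightly overstated: by about 2–5% of the median for gaps of 3 to 7 days (about 0.3–0.8 pre-dose deaths per 22-patient arm), and by at most 8–11% at the 14-day ceiling (1.2–1.6 deaths). These figures rest on exponential survival at the HMA-failure MDS medians and a common gap. The selected population probably makes them smaller. For progression the event-free wait holds in practice, because no response assessment is scheduled between registration and first dose, but the text does not formally exclude a progression documented then.

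A reader might infer that treated patients are also lost, or that the stated error rates for CR/CRi are wrong. Neither follows. Treated patients go on to event monitoring, and the binomial figures reproduce. The remaining gap for Arms B and C is that no report of non-starters by arm is planned.

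**What to change.** 1. Amend 13.7, and the matching bullet in 13.5, so that vital status and the reason for not starting are collected for every registered patient. State the schedule in Section 13 itself: 13.3, 13.5 and 13.6 send the reader to Section 18.0 for event monitoring, and that section now covers ethics.
2. Name the analysis set in 16.44 and 16.45. Keep registration as the origin for an all-registered survival analysis.
3. Time any treated-only version of 16.44 to 16.46 from first dose. This aligns the clock with the population but does not by itself recover the non-starters, so it does not replace step 1.
4. For Arms B and C, report non-starters by assigned arm with reasons, and add an all-randomised CR/CRi sensitivity analysis that counts them as non-responders.

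The cost is some SAP wording and a few vital-status calls. Reported medians and rates may come out slightly lower. The primary decision rules and sample size stay as they are. This is a cheap improvement.

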14.0 Body Fluid Biospecimens

Body Fluid Biospecimen Submission

14.1 Summary Table of Research Blood and Body Fluid Specimens to be Collected for this Protocol

Correlative Study (Section for more information)	Mandatory or Optional	Blood or Body Fluid being Collected	Type of Collection Tube (color of tube top)	Volume to collect per tube (# of tubes to be collected)	Baseline	Cycle 1 Day 2 (+/- 1 Day)	Cycle 1 Day 5 (+/- 1 Day)	Cycle 2 Day 5 (+/- 2 Day) & Day 5 of Subsequent Odd Cycles	At time of bone marrow after cycles 1 (AML only), 2 and 4 ₃ (+/- 3 days)	EOS	Process at site? (Yes or No)	Temperature Conditions for Storage /Shipping
Biomarkers	Mandatory	Whole Blood	1 x Red top 2 x Na Heparin Green top	10 mL (3)	X	X ₁	X	X	X	X	Yes	Cold Pack
Biomarkers	Mandatory	Bone marrow aspirate (if no marrow obtained whole blood becomes mandatory)	Heparinized Green top	4 mL (2)	X ₄				X	X ₂	Yes	Cold Pack
Saliva Sample	Mandatory	Saliva	n/a	n/a	X						No	ambient
Pharmacokinetics	Mandatory	Plasma	Lavender Top	2 ml			Pre-Dose, 1, 2, 4, 6, & 8 hrs post-doses	Pre-Dose			Yes	-20°C

1. Only to be done in those patients with circulating tumor cells in their blood
2. End of study bone marrow sample is optional and to be collected only if bone marrow performed as part of patient's standard of care.

3. Bone marrow aspirates will be done at times of standard clinical marrow tests. Follow Tables 4.1. (AML) and 4.2. (MDS) for study schedule. In brief after cycle 1 (for AML only, at physician's discretion can be omitted, see Table 4), after cycles 2 and 4, and then at physician discretion, an at relapse/progression. Note: there is a +/- 3 day window for marrow biopsies.
4. This is only mandatory IF a BM biopsy has not been done within 4 weeks of study start for MDS and AML and 8 weeks for MF patients.
5. Post-dose pks have a 10% window as follows: 1hr post-dose \pm 6min; 2hr post-dose \pm 12 min; 4hrs post-dose \pm 24 min; 6hrs post-dose \pm 36 min; 8 hrs post-dose \pm 48 min.

NOTE: marrow biopsies will not be done solely for the purpose of drawing a research sample, but should be performed to coincide at times of standard clinical marrow biopsies/aspirates.

14.2 Collection and Processing

- 14.21 Biomarkers: Process on site. Send all samples in original tubes to Center for Biospecimen Research & Development lab per section 14.32.
- 14.22 Pharmacokinetics: Samples are collected at the time intervals presented in the protocol. Whole blood will be collected in 2 mL BD Vacutainer tubes containing K2EDTA (lavender top) as anti-coagulant for the analysis of AZD1775. Following collection, gently invert the samples 10 times and immediately place on ice. Within 30 minutes of blood collection centrifuge at 1500 xg, at 4°C for 10 minutes. From each blood sample, transfer roughly equal volumes into a total of two 1.8 mL polypropylene cryovials using a disposable polypropylene pipette. Store plasma samples at -20°C in an upright position within 30 minutes of plasma preparation and keep frozen at this temperature until shipment and during shipment.

Labels will be provided. Tubes should be labeled with the following information: Study, Subject ID, Visit, Draw Time, and Biological Matrix (e.g., blood or plasma). When applying the label, place the label in a vertical position. Do not wrap the label around the tube horizontally. Place the label as close to the cap as possible, but do not adhere the label to the cap of the tube. Do not cover any written information with the label.

14.3 Shipping and Handling

- 14.31 Kits will be used for this study for the pharmacokinetics.

14.32 Shipping Specimens

- 14.321 For Biomarkers including saliva: Verify ALL sections of the Specimen Submission Forms (i.e. blood, bone marrow, saliva – see Forms Packet) are completed and filled in correctly.

For Pharmacokinetics: Ship the aliquots frozen on dry ice. The samples must be securely packed in boxes to avoid breakage during transit, double-bagged to contain leaks, and where applicable, packed with a sufficient quantity of dry ice to ensure they remain frozen for at least 72 hours.

Samples should be placed in a courier box with a paper copy of the Sample Inventory. Samples should be boxed up with each subject's samples in profile order and listed in the same order on the Sample Inventory for ease of checking at the bioanalytical laboratory (Covance Central Laboratory Services).

Once the courier has collected the samples, the sample receiver at Covance should be notified via email of the courier name, airway bill number, expected delivery date/time and shipment contact. An electronic sample inventory (Excel format, Request file) should also be attached to this email.

14.322 Transport specimens immediately to:

For Biomarkers:

Center for Biospecimen Research & Development
Medical Science Building
[name]
[name]
[contact]
[contact]

For Pharmacokinetics: Ship specimens via Priority Overnight service, Monday – Wednesday ONLY, to:

Covance Central Laboratory Services
Special Handling
Attn: [name]
[name]
[name]
[contact]

Do not send samples the day before, the day of, or the observed day of a national holiday.

All specimens must be shipped Monday – Wednesday ONLY.

14.4 Suggested Correlative Studies and Experiments:

The correlative studies are designed based on the pre-clinical data in AML, MDS and other tumor types and the general mechanisms of WEE1 and AraC in pathophysiology of cancer and the diseases under study. These studies are suggestions at the time of protocol development. Specific assays may change based on the current knowledge at time of biomarkers analysis.

Patients will be asked in the informed consent to provide a research bone marrow aspirate and blood samples as outlined in the schedule of events. Research bone marrow and aspirates will be collected as outlined in Table 14.1 in conjunction with a patient's standard of care bone marrow biopsy or aspirate procedures. Peripheral blood research samples will be drawn at times of routine clinical draws, in parallel with the marrow biopsies as defined in Table 14.1.

Objectives and overview of correlative studies:

The below assays and studies to be performed are suggested at the time of protocol writing. Based on novel insights into the biology of WEE1 inhibition and AML/MDS that will arise during the protocol duration, below experiments may be adjusted to reflect the current state of the art knowledge.

1. WEE1 inhibition causes DNA damage and apoptosis. The degree of DNA damage in combination with AraC is unknown. Assessment of DNA damage induction by γ H2AX and apoptosis by cleaved caspase 3 (CC3) as measured by flow cytometry on patient specimens at baseline and on follow up specimens, preferably on marrow aspirates, alternatively on peripheral blood samples will be conducted. Cell cycle distribution analysis and co-staining for total and phosphorylated CDK1/2 may be performed (using propidium iodide staining) at the same time points for samples with sufficient material.

2. Preclinical experiments ([name] Lab) suggest that the damage and cell death induction is mainly/stronger in an earlier, leukemia “stem cell like” population. Therefore the “stemness” of a γ H2AX/CC3 dual positive population will be assessed by co-staining for CD34+/38- and other hematopoietic/ leukemic stem cell surface markers in parallel with γ H2AX/CC3 by multi-color flow cytometry. Alternatively, selection of CD34+/38- cells can be performed with subsequent staining for γ H2AX/CC3.

3. In vitro we have shown that WEE1 protein expression may correlate with sensitivity to the AraC/AZD1775 combination. WEE1 protein expression levels in baseline marrow or peripheral blood may be assessed as well as WEE1 mRNA expression levels (could be deduced from RNAseq experiments below).

4. In unpublished work we have found a potential modulation of DNA damage response genes/proteins by WEE1 kinase inhibition. We will examine changes in total and phosphorylation forms of essential DNA repair proteins within the HR repair pathway, transcript genes changes under treatment with single agent AZD1775 and in the combination with AraC.

5. The role of myeloid specific mutations is unknown. Hence mutational/targeted sequencing of hematology/myeloid specific genes will be performed by targeted sequencing of gene panels or WES at baseline, at time of best response and at disease progression. Asaliva sample will be used as germline control.

6. It is hypothesized that AZD1775 activity is independent of mutated/functional p53, SETD2, ASXL-1 and RAS mutations status. Therefore all samples will be assayed by the NYU NGS for a 580 gene panel including pertinent mutations in hematological tumors. Potentially, induction of p21 in fresh samples will be assessed as a transcriptional readout of functional p53 status.

7. Next Generation Sequencing - RNA sequencing: WEE1 target genes are master transcriptional regulators. Therefore we will use next generation sequencing for RNA and microRNAs to assess transcriptional changes before, during and after therapy. Expression and differential regulation for the WEE1 published signature genes [claspin, FBXO5, MCM10, CCNE 1 and 2] in patient

specimens at baseline and follow up samples will be assessed, as well as p21 and HR pathway genes.

